9.7.13. Month 12 Continued Follow-up Procedures (Annually [± 2 weeks])

- Perform a physical examination (including smoking and alcohol consumption habits).
- Assess and record vital signs (height, weight, oral temperature, sitting heart rate, respiratory rate, and sitting blood pressure).

- Subject and Quality of Life questionnaires (see [Section 11.1.2.2](#) and [Section 12.2.6](#)).
- Perform TE (at selected study sites, where available) using the Fibroscan® TE device.
- Conduct a DEXA bone density scan (selected study sites); document whether the subject stopped taking her/his calcium supplements for 48 hours before the scan and medications for osteoporosis or osteopenia on the day of the scan, if applicable.
- Perform an endoscopy (at selected study sites, where available) to assess the presence or absence of oesophageal varix/varices.
- Perform an ultrasound for HCC surveillance (if equipment is unavailable, sites should make every attempt to use available community referral sites).
- Perform physical examination and overall status assessment for calculation of Mayo Risk Score and Child-Pugh Assessments.
 - Presence/absence of peripheral edema
 - Presence (degree)/absence of ascites
 - Presence (degree)/absence of hepatic encephalopathy
- Assess and record AEs.
- Review and record concomitant medications.
- Review and record any non-study related medical or surgical treatment procedures and any medically relevant HCP or non-HCP related office visits that have occurred since the previous study visit.
- Assess for dose titration, if eligible (refer to [Section 7.4](#)).
- Assess investigational product compliance and perform accountability.
- Assess the subject's supply of investigational product to ensure an adequate amount. Access the IWRS and dispense investigational product.
- Verify that the subject has fasted for at least 8 hours.
 - Record fasting status in the source and CRF.
 - If the subject reports having eaten within 8 hours, document accordingly in the source and CRF and remind the subject that fasting is required prior to all study visits.
- Obtain urine sample for urinalysis.
- Obtain blood samples for serum chemistry, hematology, and coagulation tests.
- Obtain blood samples for:
 - OCA, C4, and FGF-19
 - Markers of hepatic fibrosis and/or inflammation (including ELF)
 - Genetics (see [Section 11.1.2.3](#))

- Blood sample for future analysis (refer to [Section 11.1.2.3](#))

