11.1.2. Secondary Assessments

The following secondary efficacy assessments will be measured:

- Liver-related death
- Liver biochemistry (see [Table 5](#) for list of analytes to be tested)
- Biomarkers, including markers of hepatic fibrosis and/or inflammation, to be tested will include: IgM, c-reactive protein (CRP), tumor necrosis factor- α (TNF- α), FGF-19, cytokeratin-18 (CK-18) and ELF, Fibroscan (and others as determined during the course of the study).
- Data will be collected to inform quality of life and cost-effectiveness analyses that are relevant to major health care systems around the world. Quality of life will be assessed by questionnaires (PBC-40, EQ-5D-5L, and FIS) administered annually. Resource utilization information will be collected from the Medical and Surgical Treatment Procedures and Office Visit Log or other CRFs such as number, type and duration of hospitalizations, number of outpatient physician visits (subject reported), and use of concomitant medications.
- Endoscopy will be conducted at selected study sites where the device is available to assess for the presence of oesophageal varix/varices at baseline. Throughout the study, any endoscopy performed as part of the annual study assessments or standard of care will be collected in the case report form to assess for the development of varix/varices.

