13.1.5. Additional Secondary Efficacy Analyses

The following time to event secondary efficacy analyses will compare randomized OCA versus randomized placebo using the ITT population:

- Time to each component of the primary efficacy endpoint (except MELD score ≥ 15 which is captured above)
- Time to development of varix/varices
- Time to liver-related death
- Time to liver-related death or liver transplant
- Time to liver-related death, liver transplant, or MELD score ≥ 15

The same analysis methodology as used for the primary efficacy analysis will be used for these secondary efficacy analyses. Similar endpoints, where available, will be analyzed to compare OCA to historical controls as described below in [Section 13.1.8](#).

Analyses of changes in liver biochemistry (GGT, ALT, AST, conjugated bilirubin, albumin, and INR) will be summarized and analyzed using the same methodology as specified in [Section 13.1.4](#) for the key secondary analyses of change in ALP and total bilirubin.

Analyses of changes in MELD score, Child-Pugh score, Mayo Risk Score (MRS), IgM, CRP, TNF- α , FGF-19, CK-18, C4, and ELF score will be summarized and analyzed using the Wilcoxon Rank Sum Test to compare treatment groups. The median differences and 95% CI of the median differences between treatment groups will be constructed using Hodges-Lehmann estimate. If the median differences between treatments are not symmetrical around the median, the Sign Test may be used.

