 - Spontaneous bacterial peritonitis (confirmed by diagnostic paracentesis)
- Uncontrolled ascites (diuretic resistant ascites requiring therapeutic paracentesis at a frequency of at least twice in a month)
- Hepatocellular carcinoma confirmed by 2 complimentary imaging modalities

Every event for enrolled subjects will be adjudicated by an independent committee.

Primary Efficacy Analysis

The primary efficacy analysis will compare randomized OCA to randomized placebo with respect to the primary efficacy endpoint using the ITT population. The 2 treatment groups will be compared using the log rank test stratified by the randomization stratification factor. Kaplan-Meier (KM) estimates of the distribution of the time-to-event will be tabulated and graphed by treatment group. The tabulation will include the KM estimate of the medians and corresponding 95% confidence intervals (CIs), if the medians can be estimated. The number and percent of subjects censored and with events will be presented. The hazard ratio and 95% CI will be determined based on a Cox regression model stratified by randomization strata to estimate the magnitude of the effect.

Key Secondary Efficacy Analyses

The key secondary efficacy endpoints are as follows:

- Time to first occurrence of MELD score ≥ 15
- Time to liver transplant or death (all-cause)
- Change from Baseline in total bilirubin at end of study
- Change from Baseline in ALP at end of study

The key secondary efficacy analyses will compare randomized OCA to randomized placebo in ITT population with respect to the key secondary efficacy endpoints. Only adjudicated events will be included in time-to-event analyses. The comparison (hypothesis testing) will be conducted in a sequential closed testing gate-keeping procedure (in the order in which the key secondary endpoints are stated above), provided that the primary efficacy endpoint comparison is statistically significant in favor of the OCA treatment group. If the primary comparison is not statistically significant then comparison of the secondary endpoints will be considered as descriptive and exploratory.

Other Efficacy Analyses

The following secondary efficacy analyses will compare OCA to placebo on time to the following events:

- Each component of the primary efficacy endpoint (except MELD score ≥ 15 which is listed above)
- Development of varix/varices
- Liver-related death
- Liver-related death or liver transplant

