β-hCG = beta human chorionic gonadotropin; DEXA = dual-emission X-ray absorptiometry; EOS= End of Study; EOT = End of Treatment; FGF = fibroblast growth factor-19; FIS= Fatigue Impact Score; IP = Investigational Product; M = month, wk = week

^a All subjects will have the chemistry panel retested to ensure subjects have 2 ALP and bilirubin assessments at least 2 weeks apart to calculate the mean result for both analytes.

The mean of all screening ALP and bilirubin assessments will be used to determine eligibility. Samples for hematology and coagulation will not be collected at Screening Visit 2.

^b The subject should be contacted by telephone on a monthly basis in between at-clinic study visits at Month 1 and Month 2 (±1 week), and also 2 weeks post dose titration (up or down), to assess for AEs and concomitant medications and to verify that s/he is dosing as directed.

^c As soon as possible upon study discontinuation and as near as possible to last dose taken.

^d Visits should be based on Day 0 (not on the prior visit).

^e Medical history at Screening and the yearly physical exam will include an assessment of smoking and alcohol consumption history and current habits for both.

^f Height will be collected at this visit.

^g The EQ-5D-5L and FIS Quality of Life questionnaires are validated for use in multiple languages. If a validated translation is not available in the local language required for a specific study subject, the data from that questionnaire will not be collected (See Section 11.1.2.2 and Section 12.2.6).

^h Transient elastography (TE) will be conducted at selected study sites where the Fibroscan® TE device is available. Similarly, DEXA will be conducted at selected study sites where the DEXA device is available. Please refer to Section 9.7.4 for additional information related to the allowed windows at Day 0 for these specific procedures.

-
- ⁱ Endoscopy will be conducted at selected study sites where the device is available to assess for the presence of oesophageal varix/varices. Please refer to [Section 9.7.4](#) for additional information related to the allowed window at Day 0 for this specific procedure.
 - ^j Ultrasound will be conducted to enhance HCC surveillance. If a lesion is found, a second confirmatory image (eg, MRI) should be obtained. Please refer to [Section 9.7.4](#) for additional information related to the allowed windows at Day 0 for this specific procedure

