9.7.4. Day 0 Procedures (Randomization)

- Review inclusion and exclusion criteria for eligibility.
- Assess and record vital signs (weight, oral temperature, sitting heart rate, respiratory rate, and sitting blood pressure).
- Subject and Quality of Life questionnaires (see [Section 11.1.2.2](#) and [Section 12.2.6](#)).
- Perform transient elastography (TE; at selected study sites, where available) using the Fibroscan[®] TE device. If TE has been done within 6 months of Day 0 and a report/adequate data are available, a pretreatment TE at Day 0 is not required. If the TE cannot be performed on Day 0 (e.g., device/technician unavailability, scheduling issues, etc), the procedure may be completed within the screening visit window, as close as possible to the Day 0 visit, after subject eligibility has been confirmed.
- Conduct a DEXA bone density scan (at selected study sites, where available); document whether the subject stopped taking her/his calcium supplements for 48 hours before the scan and medications for osteoporosis or osteopenia on the day of the scan, if applicable. If DEXA has been done within 12 months of Day 0 and a report/adequate data are available, a pretreatment DEXA at Day 0 is not required. If the DEXA cannot be performed on Day 0 (e.g., device/technician unavailability, scheduling issues, etc), the procedure may be completed within the screening visit

window, as close as possible to the Day 0 visit, after subject eligibility has been confirmed.

- Perform an esophagogastroduodenoscopy (endoscopy; at selected study sites, where available) to assess the presence or absence of oesophageal varix/varices. If an endoscopy has been done within 12 months of Day 0 and a report/adequate data are available, a pretreatment endoscopy at Day 0 is not required. If the endoscopy cannot be performed on Day 0 (e.g., device/technician unavailability, scheduling issues, etc), the procedure may be completed within the screening visit window, as close as possible to the Day 0 visit, after subject eligibility has been confirmed.
 - Subsequent endoscopies should be performed annually or per standard of care and the Investigator's clinical judgment throughout the course of the study.
Endoscopies should also be performed when platelet counts are $<150 \times 10^9/L$.

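### Time to varices is analysed in all ITT subjects although follow-up endoscopy may be yearly, by standard of care or platelet-triggered, so unequal triggering between arms could produce a spurious difference

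*Protocol*

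**What the plan says.** The follow-up endoscopy rule is written in two ways.

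- **Section 9.7.4 (Amendment 1.1):** "Subsequent endoscopies should be performed annually or per standard of care", with the investigator's judgment also named as a basis. The next sentence reads "Endoscopies should also be performed when platelet counts are" below 150 × 10^9/L. Both sit under the selected-sites endoscopy instruction, and the text does not say whether the platelet rule is confined to those sites.
- **Table 1 (Section 7.1.2) and the visit lists:** endoscopy is marked at Day 0, Month 12 and each later annual visit, but not at EOT/EOS. The footnote reads "Endoscopy will be conducted at selected study sites where the device is available to assess for the presence of oesophageal varix/varices". Section 9.7.13 repeats it for the annual visit: "Perform an endoscopy (at selected study sites, where available) to assess the presence or absence of oesophageal varix/varices".

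The endpoint appears in the Amendment 1.1 synopsis as "Development of varix/varices" and in Section 13.1.5 of Amendment 1 as "Time to development of varix/varices". Section 13.1.5 applies the primary endpoint's methods (stratified log rank, Kaplan-Meier, stratified Cox) in the ITT population. Section 13.1.10.1 censors event-free subjects at last contact. Section 11.1.2 states that "any endoscopy performed as part of the annual study assessments or standard of care will be collected in the case report form" to assess development of varices. Section 13.1.11 makes tests outside the hierarchy descriptive and exploratory, and varices is outside it.

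The Amendment 1.1 text at hand breaks off in Section 9.7, so Sections 9.7.13, 11.1.2 and 13 are cited from Amendment 1.

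**The concern.** A varix is seen only when someone looks, so the recorded event time is a detection time. Three features of the plan tie detection to things that happen after randomization.

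1. Under Section 9.7.4, how often a subject is examined may depend on usual care, investigator judgment and the platelet count. Haematology is drawn at the quarterly visits, so the trigger can fire between annual visits.
2. The analysis covers all ITT subjects, but scheduled endoscopy exists only at selected sites. Elsewhere a subject is examined only if clinically scoped.
3. Censoring at last contact credits a subject never scoped after baseline with varix-free time up to that contact, and no endoscopy at EOT/EOS recovers what was missed.

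If one arm reached the platelet threshold less often, it would be scoped less often and fewer of its varices would be found. Log rank and Cox cannot tell fewer varices from fewer endoscopies. Blinding limits differences that come from the investigator, but not those that come from a laboratory value.

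**Working it through.** The plan gives no varix incidence, no platelet rate and no design figure for this endpoint. Its 121-event calculation concerns the primary composite and has no bearing here. Every rate below is therefore an assumption.

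**Model 1: apparent rate ratio when the true ratio is 1.00.**

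Inputs:
- Varix onset 0.04/year in both arms over 7 years, so true incidence is 1 − exp(−0.04 × 7) = 24% in each arm.
- First platelet trigger 0.06/year on placebo and 0.05, 0.04 or 0.03/year on OCA. The trigger hazard ratios are 0.05/0.06 = 0.83, 0.04/0.06 = 0.67 and 0.03/0.06 = 0.50.
- Share ever triggered by year 7, from 1 − exp(−7λ): 34% on placebo; 30%, 24% and 19% on OCA.
- Endoscopies occur at the trigger and yearly after it, at random at a background care rate, and yearly for any subjects on routine scheduling.
- Detection time is the first endoscopy at or after onset. The apparent ratio is the OCA rate of detected varices per subject-year divided by the placebo rate.

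| Assumed follow-up endoscopy | Trigger HR 0.83 | 0.67 | 0.50 |
|---|---|---|---|
| None yearly; background 0.05/year | 0.91 | 0.82 | 0.71 |
| None yearly; background about every 3 years | 0.98 | 0.95 | 0.93 |
| Half yearly; rest 0.05/year | 0.98 | 0.95 | 0.91 |
| Three-quarters yearly; rest 0.05/year | 0.99 | 0.98 | 0.97 |
| All yearly | 1.00 | 1.00 | 1.00 |

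Repeat runs move individual cells by about 0.01. With equal triggering (HR 1.0) the ratio is about 1.00 in every row.

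**Model 2: false-positive rate of the two-sided 5% log rank test, no true effect.**

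Inputs: onset 6%/year in both arms; platelets falling below the threshold at 8%/year on placebo; follow-up 6 to 8 years; onset and trigger correlated at 0.5 (0 also run for part of the grid); 3,000 trials per cell. Sizes are 350 subjects and 176, the latter standing for selected sites only.

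| Assumed follow-up endoscopy | Trigger HR | n = 350 | n = 176 | Apparent HR |
|---|---|---|---|---|
| Trigger only | 0.6 | 25–28% | 14–17% | 0.63–0.73 |
| Trigger only | 0.8 | 8.4% | 6.6% | about 0.87 |
| Half yearly, rest trigger only | 0.6 | 8.9% | 6.5% | about 0.88 |
| Three-yearly care plus trigger | 0.6 | about 5% | about 5% | 0.98–0.99 |
| All yearly plus trigger | 0.6 | about 5% | about 5% | about 1.00 |
| Any of these schedules | 1.0 | about 5% | about 5% | about 1.00 |

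The two models agree. A spurious difference needs both a substantial share of subjects without routine endoscopy and a difference in triggering between arms. Remove either and it disappears.

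**The case against.** Four points count against giving this much weight.

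- **The large figures come from an extreme corner.** A ratio of 0.71 needs half the trigger hazard on OCA and background endoscopy about once in 20 years with nobody scoped yearly. Table 1 shows yearly endoscopy, and if that is followed the distortion is negligible. This stands, and it is why the full range is given.
- **The arm difference is assumed.** The protocol reports no OCA effect on platelets. It credits OCA with anti-fibrotic properties (Section 5.2), which makes an effect conceivable but does not show one. A drug that altered platelet decline might also alter varices. This stands too: the case is conditional.
- **Section 11.1.2 does not name platelet-triggered endoscopies.** A reader might infer that they all count toward the endpoint. The text names annual and standard-of-care endoscopies only; nothing visible excludes triggered ones, but their inclusion is an inference.
- **The endpoint is exploratory, and detail can be left to the SAP.** The first part limits the weight of the point. The second answers it only in part, because the protocol itself fixes the population, the test and the censoring rule, and its two schedule statements conflict.

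**Conclusion.** The point holds in conditional form. Section 9.7.4 and Table 1 do not give the same follow-up schedule and must be reconciled; which clinical schedule is right is not a question for this point. As written, the analysis counts unscoped subjects as varix-free and lets detection depend on a post-randomization laboratory value.

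With equal true incidence and an assumed trigger hazard ratio of 0.83 to 0.5, the apparent rate ratio is about 0.91 to 0.71 if almost nobody is scoped routinely. It is 0.98 to 0.91 if half are scoped yearly or care is three-yearly, and about 1.00 if all are scoped yearly or triggering is equal by arm. All rates are assumptions.

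A reader might go further and infer that the plan is biased toward OCA, or that any observed varices difference would be an artefact. The documents do not support that: they give no arm difference in platelets and no evidence that sites depart from yearly endoscopy. The primary endpoint, the key secondary endpoints and study-wise type I error are unaffected.

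**What to change.** Reconcile Section 9.7.4 with Table 1 and the visit lists, and state which endoscopies contribute to the endpoint. In Section 13.1.5:

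1. Base the main time-to-varices analysis on subjects at sites doing the scheduled yearly endoscopy who have a varix-free baseline endoscopy. Define this by site, not by the examinations individual subjects went on to have, so that the randomized comparison is kept.
2. Censor at the last endoscopy rather than last contact.
3. Use an interval-censored or discrete-time model stratified by the randomization factors. Count a varix found at an interim endoscopy in the yearly interval that contains it. An early look then largely ceases to matter, because the next scheduled endoscopy would place the varix in the same interval.
4. Report the ITT analysis using all endoscopies as a sensitivity analysis, with endoscopies per subject-year by arm so that any difference in ascertainment is visible.

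The cost is protocol wording, fewer subjects and less precision for one exploratory endpoint. The analysis change asks for no additional endoscopy, and clinically indicated endoscopy is unchanged.

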9.7.6. Month 3 Procedures

- Assess and record vital signs (weight, oral temperature, sitting heart rate, respiratory rate, and sitting blood pressure).
- Assess and record AEs.
- Review and record concomitant medications.
- Review and record any non-study related medical or surgical treatment procedures and any medically relevant HCP or non-HCP related office visits that have occurred since the previous study visit.

- Assess investigational product compliance and perform investigational product accountability.
- Assess for dose titration, if eligible (refer to [Section 7.4](#)).
- Verify that the subject has fasted for at least 8 hours.
 - Record fasting status in the source and CRF
 - If the subject reports having eaten within 8 hours, document accordingly in the source and CRF and remind the subject that fasting is required prior to all study visits, but water is permitted.
- Obtain blood samples for serum chemistry, hematology, and coagulation tests.
- Obtain blood samples for:
 - OCA, C4, and FGF-19
- Schedule the next visit and assess the subject's supply of investigational product to ensure an adequate amount. Access the IWRS and dispense investigational product if necessary.
- Schedule the next visit, reiterate dosing instructions, and advise the subject:
 - NOT to take investigational product on the morning of the next visit, and
 - To bring the investigational product bottle(s); s/he will dose at the clinic, and
 - To fast overnight (at least 8 hours) prior to the next visit. Fasting is required prior to all study visits, but water is permitted.

9.7.7. Month 6 Procedures

- Assess and record vital signs (weight, oral temperature, sitting heart rate, respiratory rate, and sitting blood pressure).
- Subject questionnaires (see [Section 12.2.6](#))
- Assess and record AEs.
- Review and record concomitant medications.
- Review and record any non-study related medical or surgical treatment procedures and any medically relevant HCP or non-HCP related office visits that have occurred since the previous study visit.
- Assess investigational product compliance and perform investigational product accountability.
- Assess for dose titration, if eligible (refer to [Section 7.4](#)).
- Assess the subject's supply of investigational product to ensure an adequate amount. Access the IWRS and dispense investigational product if necessary.
- Perform physical examination and overall status assessment for calculation of Mayo Risk Score and Child-Pugh Assessments.

- Presence/absence of peripheral edema
- Presence (degree)/absence of ascites
- Presence (degree)/absence of hepatic encephalopathy
- Verify that the subject has fasted for at least 8 hours.
 - Record fasting status in the source and CRF.
 - If the subject reports having eaten within 8 hours, document accordingly in the source and CRF and remind the subject that fasting is required prior to all study visits.
- Obtain blood samples for serum chemistry, hematology, and coagulation tests.
- Obtain blood samples for:
 - OCA, C4, and FGF-19
 - Markers of hepatic fibrosis and/or inflammation (including ELF)
 - Blood sample for future analysis (refer to [Section 11.1.2.3](#))
- Schedule the next visit, reiterate dosing instructions, and advise the subject:
 - NOT to take investigational product on the morning of the next visit, and
 - To bring the investigational product bottle(s); s/he will dose at the clinic, and
 - To fast overnight (at least 8 hours) prior to the next visit. Fasting is required prior to all study visits, but water is permitted.
- For subjects who will participate in the PK assessment and are taking BAS or aluminum hydroxide- or smectite-containing antacids, they should be instructed to not take their regular dose on the morning of the study visit.

